3. STUDY OBJECTIVES

3.1. Primary Objective:

- **Efficacy:** To evaluate the relative efficacy of oral CAB/CAB LA (oral run-in and injections, Steps 1 and 2) vs. daily oral TDF/FTC for HIV prevention (Steps 1 and 2).
- **Safety:** To evaluate the relative safety of oral CAB/CAB LA (oral run-in and injections, Steps 1 and 2) vs. daily oral TDF/FTC for HIV prevention (Steps 1 and 2).

3.2. Secondary Objectives:

- To compare HIV incidence among participants receiving oral CAB/CAB LA vs. daily oral TDF/FTC (Steps 1, 2 and 3).
- To evaluate relative efficacy of oral CAB/CAB LA vs. oral TDF/FTC in subgroups defined by the baseline factors of age, herpes simplex virus-2 (HSV-2) serostatus, contraceptive method, and body mass index (BMI).
- To describe and model the relationship between HIV incidence and drug concentration, within each arm.
- To describe the distribution and correlates of drug concentration, within each arm.
- To compare the acceptability of and preferences for CAB LA vs. oral TDF/FTC.

3.3. Tertiary Objectives:

- To estimate sexual risk behaviors, as measured by self-report and rates of incident sexually transmitted infections (STIs).
- To compare Grade >2 adverse event (AE) rates in women with baseline BMI $</\geq 30 \text{ kg/m}^2$, within each study arm.
- To compare differences in weight gain and BMI, by arm.
- To compare pregnancy incidence and outcomes between arms.
- To evaluate rates of HIV drug resistance among participants who acquire HIV infection during the study among participants receiving oral CAB/CAB LA vs. oral TDF/FTC.
- To determine plasma concentrations of medroxyprogesterone (DMPA) or norethisterone (NET-EN) or etonogestrel when co-administered with CAB LA.

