6.3 Modified ITT (mITT) Population

All women who are included in the ITT Population and who were not HIV infected at enrollment are included in the mITT population.

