6.14 Seroconverter Population

All ITT participants who, during the course of the trial, are either identified to have been HIV infected prior to randomization, or who acquired HIV infection during trial the primary analysis follow-up period.

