6.15 Primary Seroconverter Population

All ITT participants who are HIV-uninfected at randomization and acquire HIV infection during the primary analysis follow-up period.

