Data from steps 1 and 2 (PRIMARY mITT dataset) will be used. Tables will summarize the number of pregnancies and pregnancy rate by arm. The pregnancy rate and 95% robust confidence interval for each treatment arm will be calculated using a log-linear model for counts using log(person-time) (excluding time spent pregnant) as an offset, assuming a Poisson distribution, and using a robust variance (i.e. generalized estimating equations).

Outcomes of all detected pregnancies (PREGNANCY dataset) and all confirmed pregnancies (CONFIRMED PREGNANCY dataset), including information of drug exposure during the conception period and pregnancy period, will be tabulated by arm.

e. **Objective:** To evaluate rates of HIV drug resistance among participants who acquire HIV infection during the study among participants receiving oral CAB/CAB LA vs. oral TDF/FTC.

Population: Primary SEROCONVERTER Population

Data from steps 1, 2 and 3 will be included. The number of cases of drug resistance will be summarized by arm and step. All cases of drug resistance among incident HIV infections during the study will be described.

f. **Objective:** To determine plasma concentrations of medroxyprogesterone (DMPA) or norethisterone (NET-EN) or etonorgestrel (from implants) when co-administered with CAB LA.

Population: CONTRACEPTION Subgroup Population

Outcome: Plasma concentration of medroxyprogesterone or norethisterone.

Boxplots of plasma concentrations of DMPA/NET_EN/etonorgestrel will be generated by arm. For women in the CAB-LA arm, a plot of plasma concentrations versus time since last injection will be plotted and a smooth line will be fit through the data. Proportion of women with plasma concentrations below 0.1 ng/mL (DMPA) or TBD (NET_EN) or 90pg/mL (etonorgestrel) will be reported and compared (separately, for women using each drug) between arms using a Fisher's exact test or a permutation test if multiple observations are available on each woman.

In addition, we will compare mean contraceptive drug levels (and/or other PK parameters) between the CAB LA and TDF/FTC arms for each contraceptive subgroup using a t-test (or a t-test with robust variance if multiple observations on each woman are available).

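### The resistance analysis in SAP 7.3.7 e covers Steps 1 to 3 by step, but its named population holds only infections acquired in the primary (Steps 1 and 2) period

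*SAP*

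**What the plan says.** The tertiary objective in SAP Section 3.3, repeated in 7.3.7 e, is "To evaluate rates of HIV drug resistance among participants who acquire HIV infection during the study". Section 7.3.7 e sets the data scope and layout: "Data from steps 1, 2 and 3 will be included. The number of cases of drug resistance will be summarized by arm and step". It closes with "All cases of drug resistance among incident HIV infections during the study will be described".

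The population line in the same item reads "Population: Primary SEROCONVERTER Population". Section 6.15 defines that population as "All ITT participants who are HIV-uninfected at randomization and acquire HIV infection during the primary analysis follow-up period".

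The primary follow-up period is fixed elsewhere. Section 4.1 bases the primary analysis on incidence in Steps 1 and 2, and Section 7.3.1 censors the primary outcome when Step 2 ends. Appendix B excludes infections outside the analysis timeframe from the primary endpoint. If there is a study-wide move to Step 3, Appendix B cuts the data at the transition date, with an unanswered query about adding one month.

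Section 6.14 defines the wider Seroconverter Population. It opens by referring to the whole trial but ends in a garbled clause: "or who acquired HIV infection during trial the primary analysis follow-up period".

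**The concern.** The population line and the rest of 7.3.7 e cannot both be applied. A woman first infected in Step 3 belongs to the objective, the data scope, the by-step layout and the closing sentence, but not to the named population. A programmer who filters on that population would produce a by-arm, by-step table with few or no Step 3 infections, while the case descriptions were still meant to include them.

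Step 3 is a period where such a table is of interest. Section 2.7.3 gives open-label TDF/FTC there to cover the pharmacokinetic tail in Arm A, and it plans for confirmed infections during that step. The outputs would also fail to reconcile: the Steps 1 to 3 incidence analysis in 7.3.6 a uses the mITT population and would count Step 3 infections that the resistance table leaves out.

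**Working it through.** There is no stated figure to reproduce; the check is mainly a comparison of definitions.

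**Scope against population**

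| Element | Source | Period |
|---|---|---|
| Objective | 3.3, 7.3.7 e | Whole study |
| Data and layout | 7.3.7 e | Steps 1, 2 and 3, by step |
| Case descriptions | 7.3.7 e | Whole study |
| Named population | 6.15 | Primary analysis follow-up |
| Primary analysis follow-up | 4.1, 7.3.1 | Steps 1 and 2 |

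The last two rows together exclude infections acquired in Step 3. The preceding item, 7.3.7 d, uses the label in the same sense: "Data from steps 1 and 2 (PRIMARY mITT dataset) will be used".

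**Does Section 6.14 supply the missing population?** No. Its closing clause points back to the primary period, and it adds women infected before randomization, who are not incident cases.

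**Could the queried extra month in Appendix B rescue it?** Take a woman whose Step 3 Day 0 falls on or after the transition date. Appendix A gives these windows, in days from Step 3 Day 0:

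- Week 12: opens day 43, target day 84
- Week 24: opens day 127
- Week 36: opens day 211
- Week 48: opens day 295

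One month ends by day 31 at the latest, and 43 − 31 = 12, so it stops at least 12 days before the Week 12 window opens. Appendix B counts a primary endpoint by the date of the first positive visit. Weeks 12, 24, 36 and 48 therefore fall outside, which is 4 of the 5 scheduled Step 3 visits. Only Day 0 or an unscheduled visit could fall inside.

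**Same check with the midpoint date.** Appendix B uses the midpoint between the last negative and first positive visits for study time. After a negative Day 0 test:

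- Week 12 at target: (0 + 84)/2 = day 42, outside.
- Week 12 at its earliest: (0 + 43)/2 = day 21.5, inside. The midpoint stays within 31 days only if the visit is by day 62, since 62/2 = 31.
- Week 24 at its earliest, with Week 12 missed: (0 + 127)/2 = day 63.5, outside.

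Under this more generous reading only early Week 12 detections are recovered.

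**Is the base population affected?** No. Section 6.15 starts from ITT women uninfected at randomization. Section 6.3 defines mITT in equivalent terms: "All women who are included in the ITT Population and who were not HIV infected at enrollment are included in the mITT population". Only the time span differs.

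**The case against.** The strongest reply is that the intent is plain. The objective, data line, layout and closing sentence all point to Steps 1 to 3; only one label is off, and the closing sentence should keep Step 3 cases in the report. The analysis is tertiary, descriptive and untested, and Section 9.2 lists no resistance table for the Clinical Study Report. All of this stands and limits the weight of the point. It does not remove the conflict: the population line is the instruction a programmer filters on, and table and descriptions could then disagree.

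A second reading takes the Steps 1 to 3 data to mean later samples from women infected in Steps 1 and 2. That does not fit an objective about infection acquired during the study.

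Third, women who stop injections early stay in primary follow-up for their originally scheduled Steps 1 and 2 (Section 7.3.1). Some infections in the pharmacokinetic tail are therefore already captured. This is correct, but it does not help those who enter Step 3 at the transition.

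Fourth, the word primary is not used consistently: the safety population in Section 6.6 carries it with no limit by step. So 7.3.7 d is only supporting evidence, and the case rests on 6.15 read with 4.1 and 7.3.1.

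Fifth, the visit count applies only to a study-wide transition. Appendix B has another branch, for no such transition or an early stop, which censors at study closure and mentions no extra month. The count is not claimed for that branch.

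**Conclusion.** The concern holds. As written, the population named in 7.3.7 e contradicts the section's own objective, data scope and layout, and Section 6.14 offers no clear substitute. Applied literally, it drops infections first found after the transition to Step 3 from the by-arm, by-step table, apart from any caught by the unresolved extra month.

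No case count is given. The SAP states neither Step 3 incidence nor resistance rates, and design rates assumed for the blinded arms need not apply when both arms take open-label TDF/FTC. The supportable measure is that 4 of 5 scheduled Step 3 visits lie outside the primary period with or without the extra month. This assumes a study-wide transition, Step 3 Day 0 on or after that date, and classification by first positive visit. Primary and secondary inference is unaffected. The text should be corrected before the table is programmed.

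**What to change.** In 7.3.7 e, replace the population line with: all mITT participants with an EAC-confirmed incident HIV infection in Steps 1, 2 or 3, tabulated by arm and by the step of the first HIV-positive visit as determined by the EAC.

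Add a note that this classifies by detection, not acquisition, in line with the Appendix B endpoint rule. An infection acquired late in Step 2 but first positive in Step 3 would appear under Step 3. Visit 33.0 follows Appendix A, which lists it as Step 3 Day 0. Visit codes on the open-label, pregnancy and annual schedules carry no step, so the programming specification needs an assignment rule for them; the existing by-step layout already requires one.

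Correct Section 6.14 so that it states a single period.

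The cost is one population line with its note and one wording correction. No new data are needed, because 7.3.7 e already plans to use Steps 1 to 3. The incidence analysis in 7.3.6 a already carries the primary definition of HIV detection through Step 3. Primary censoring does not change.

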8. MISSING DATA AND IMPUTATIONS

Data may be missing due to participant dropout, participant nonresponse, or due to failures in data collection. In general, the last category (failures in data collection) is quite rare in HPTN trials. Further, it is common to assume that such data are missing completely at random (MCAR) (Rubin DB. *Biometrika* 1976; 63:581–592) and so will not bias results. However, participant dropout and/or nonresponse are unlikely to be MCAR and so attention must be paid to the potential for bias if there are high levels of missing data for these reasons. Here we discuss the approaches we will take for analyses in the presence of missing data.

For the primary endpoints, HIV infections and safety events, and other biological endpoints the primary cause of missing data is participant dropout. Historically, HPTN trials have had good retention of participants and we expect that to be the case for this trial. Therefore, analyses will be conducted assuming uninformative censoring. If loss-to-follow-up is low and similar between the arms we will not conduct any additional sensitivity analyses. However, if loss-to-follow-up is greater than 20% or meaningfully different between arms (>5%-points), then we will investigate the sensitivity of the results to assumptions about the missing data. Specifically, we will use inverse probability-of-censoring weights to adjust for loss-to-follow-up (Cain LE. *Stat Med* 2009; 28:1725-1738) and compare the adjusted treatment effect to the unadjusted treatment effect.

Behavioral and self-reported endpoints (e.g. acceptability) may be subject to participant nonresponse. The analyses described below are based on a complete-case approach. However, if non-response is high (>15%) or differential between arms (> 5%-points) then we will perform sensitivity analyses using multiple imputation. Baseline data will be used to develop the imputation model and standard errors will be adjusted using Rubin's method (Rubin DB. *Multiple Imputation for Nonresponse in Surveys*, Wiley, New York, 1987). Both complete case and multiple imputation results will be reported.

8.1. Missing Start and Stop Dates for Prior and Concomitant Medication, and Medical History

The Assumption is to consider the most conservative judgment when imputing.

Start date:

When imputing a start date ensure that the new imputed date is sensible i.e. is prior to the end date and the general rules are:

- i. If start date is completely missing, start date will not be imputed
- ii. If year and month are present and day is missing, set day to the 1st day of month.
- iii. If year and day are present and month is missing, then set month to January.
- iv. If year is present and month and day are missing, set month and day to January 1st.

Stop date:

- i. If end date is completely missing, end date will not be imputed
- ii. If year and month are present and day is missing, set day to the last day of month.
- iii. If year and day are present and month is missing, set month to December

- iv. If year is present and month and day are missing, set month and day to December 31st.

8.2. Missing Start and Stop Dates for Adverse Events

The Assumption is to consider the most conservative judgment when imputing.

Start date:

1. If start date is completely missing, start date is set to date of first dose.
2. If (year is present, and month and day are missing) or (year and day are present, and month is missing):
 - a. If year = year of first dose, then set month and day to month and day of first dose.
 - b. If year < year of first dose, then set month and day to December 31st.
 - c. If year > year of first dose, then set month and day to January 1st.
3. If month and year are present and day is missing:
 - a. If year = year of first dose and
 1. If month = month of first dose, then set day to day of first dose date.
 2. If month < month of first dose, then set day to last day of month.
 3. If month > month of first dose, then set day to 1st day of month.
 - b. If year < year of first dose, then set day to last day of month.
 - c. If year > year of first dose, then set day to 1st day of month.

Stop date:

If the outcome of the AE was ongoing or unknown, then the rules outlined below will not be applied.

1. If stop date is completely missing, stop date is set to date of study discontinuation.
2. If (year is present, and month and day are missing) or (year and day are present, and month is missing):
 - a. If year = year of study discontinuation, then set month and day to month and day of study discontinuation.
 - b. If year < year of study discontinuation, then set month and day to December 31st.
 - c. If year > year of study discontinuation, then set month and day to December 31st.
3. If month and year are present and day is missing:
 - a. If year = year of study discontinuation and
 - i. If month = month of study discontinuation, then set day to day of study discontinuation date
 - ii. If month < month of study discontinuation, then set day to last day of month.
 - iii. If month > month of study discontinuation, then set day to last day of month.
 - b. If year < year of study discontinuation, then set day to last day of month.
 - c. If year > year of study discontinuation, then set day to last day of month.

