7.3.2. Primary Safety Analysis

Objective: To evaluate the relative safety of oral CAB/CAB LA (oral run-in and injections, Steps 1 and 2) vs. daily oral TDF/FTC for HIV prevention (Steps 1 and 2).

Population: Safety population

The primary pre-specified safety comparison between arms will be based on all AEs with maximum grade ≥ 2 . In general, formal statistical comparison of individual types of safety events across arms is not planned since interpretation of differences must rely heavily upon clinical judgment. Where formal statistical testing is considered necessary to guide judgement of observed differences for any single event or collection of events, differences in events grade 2 and higher will be assessed. The event rate and 95% robust confidence interval for each treatment arm will be calculated using a log-linear model for counts using log(person-time) as an offset, treatment as a covariate, assuming a Poisson distribution and using a robust variance (i.e. generalized estimating equations). Event rates will be compared between treatment arms using this same model. Event rates will be compared between treatment arms using this same model and a type I error rate of $\alpha=0.05$ is prespecified. Very rare events will be compared using an exact Poisson test. Additional supporting descriptive safety analyses will be presented.

For Safety OBSP analysis, adverse event follow-up will be censored after the last injection before a termination or a permanent product discontinuation regardless of any delays in injections. If termination or a permanent product discontinuation occurs prior to their first injection, the participant's follow-up time will be censored at the termination or permanent product discontinuation date +1. If termination or a permanent product discontinuation occurs after the first injection, the participants follow-up time will be censored up through 6 weeks after the Week 5 injection, if that is the last injection, or 10 weeks after the last injection for subsequent injections.

7.3.3. Adverse events in Step 1

Objective: To compare the safety of oral CAB vs. oral TDF/FTC in Step 1

Population: Primary Safety

Censoring: AEs are censored at 120 days after randomization for participants who never received an injection; at 1 day after the date of termination or investigational product discontinuation; at date of first injection, whichever occurs first. Reported AEs will be excluded if they occur after the censoring time.

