7.3.4. Adverse events Step 2 only OBSP

Objective: To compare the safety of CAB LA vs. oral TDF/FTC proximal to blinded study drug administration

Population: Step 2 safety

Censoring: AEs are censored using ON BLINDED STUDY PRODUCT (OBSP) censoring.

Details of the OBSP censoring definitions are given in Appendix B. Reported AEs will be excluded if they occur before the first injection or after the OBSP censoring time.

Descriptive and Statistical Analysis will be performed as above

7.3.5. *Laboratory evaluations*

Population: Primary Safety

Descriptive: Laboratory findings for CBC, chemistries (urea, creatinine, CPK, glucose, calcium, phosphorous, amylase, lipase), liver function (AST, ALT, total bilirubin, alkaline phosphatase) and fasting lipid profile (total cholesterol, triglycerides, HDL, LDL) will be reported by grade, as defined in the “Division of AIDS (DAIDS) Table for Grading the Severity of Adult and Pediatric Adverse Events”. The proportion of laboratory findings qualifying as Grade 2 or above will be presented. Laboratory values will be reported by arm as median, 1st and 3rd quartiles, min and max, and (at follow-up visits) as median, 1st and 3rd quartile change from baseline (see below). Summaries involving values and changes from baseline at scheduled visit time points will consider values from scheduled visits only, and in the case of missing values, results will not be carried forward from interim (unscheduled) visits. For summaries and analyses involving changes in laboratory values over time or maximum change from baseline (e.g. shift tables), values from interim (unscheduled) visits will also be considered.

Formal comparisons of laboratory values will be conducted as follows:

- Absolute values: A mixed-effects model with participant as the random effect and site and arm as fixed effects will be used to assess overall differences in each laboratory outcome by arm. Outcomes with highly skewed distributions will be log-transformed. A continuous time (elapsed study time) term and an interaction of time with study arm will be added to model time trends in laboratory values that may emerge with continuous exposure to study drug. Only post baseline visits will be included.

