Laboratory results will be summarized by scheduled study visit. Summary calculations such as maximum post-baseline level will include data from interim (unscheduled visits). Formal comparisons of laboratory findings between arms will not be included in the CSR.

- **Adverse Events**

The reporting of safety data is descriptive and will include all subjects who receive at least one dose of investigational product. AEs will be summarized based on the frequency of AEs and their severity for all treated subjects. All AEs will be coded using Medical Dictionary for Regulatory Activities (MedDRA) and summarized by treatment group. Data will be summarized using preferred term and primary system organ class.

If a subject experiences multiple events that map to a single preferred term, the greatest severity will be assigned to the preferred term for the appropriate summaries.

Summaries of AEs will include any AEs reported beginning with the first dose of investigational product on Day 1. The occurrence of adverse events will be summarized by treatment group using preferred terms, system organ classifications, and severity. Separate summaries of serious adverse events, adverse events related to investigational product, and events leading to the discontinuation of investigational product will be generated. All adverse events reported will be listed for individual subjects showing both verbatim and preferred terms.

- **Efficacy and Efficacy Subgroups**

In the Clinical Study Report, primary efficacy analysis will be presented as described in Section 7.3.1. For subgroup analyses, the age and BMI subgroup analyses will be presented in the Clinical Study Report, but analyses considering contraceptive use and HSV-2 status at baseline will not be presented in the Clinical Study Report.

10. Summary of changes

10.1 Version 3.0 was prepared during the planning process for the Clinical Study Report. The blinded statistician continued to not have access to individual level data.

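### SAP section 8.2 imputes partial AE start dates from the first oral dose only, so AEs that may have followed the first injection are assigned to Step 1

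*SAP*

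**What the plan says.** SAP section 8.2 opens with a principle: "The Assumption is to consider the most conservative judgment when imputing". Its start-date rules then use one reference point, the first dose.

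- Day missing, same month as the first dose: "If month = month of first dose, then set day to day of first dose date".
- Day missing, later month of the same year: "If month > month of first dose, then set day to 1st day of month".
- Day missing, later year: "If year > year of first dose, then set day to 1st day of month".
- Month missing, with or without the day: "If year = year of first dose, then set month and day to month and day of first dose".
- No date at all: the date of first dose.

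Section 8.2 does not define the first dose. Section 9.2 does so in effect: "Summaries of AEs will include any AEs reported beginning with the first dose of investigational product on Day 1". Under section 2.7 the first product is oral and is taken for five weeks before any injection.

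Two safety analyses sort AEs by onset relative to the first injection. Section 7.3.3 (Step 1) censors at the earliest of several dates, the last being "at date of first injection, whichever occurs first", and excludes only AEs after that point. Section 7.3.4 (Step 2) states: "Reported AEs will be excluded if they occur before the first injection or after the OBSP censoring time".

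**The concern.** The regimen has two starts, oral and injectable, but the imputation recognizes only one. For the oral start the rules do what the stated principle promises: an AE of uncertain day in the first-dose month is treated as arising on treatment. For the injectable start they do the reverse: an AE of uncertain day in the first-injection month is treated as arising before the injection.

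The step-specific analyses are at stake. Section 7.3.4 exists to compare safety close to blinded study drug administration, and Appendix E singles out events of interest in relation to injections. An AE that followed the first injection but has a partial date can be removed from that analysis and charged to the comparison of oral CAB with oral TDF/FTC.

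**Working it through.** The plan gives no figure on this point to reproduce. The check applies the rules of 8.2 to the trial calendar.

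**Inputs.** The lag from first oral dose to first injection is five weeks, or 35 days (2.7.1). The rules are those of 8.2, 7.3.3 and 7.3.4. Assumptions: first-dose dates, injection days and onset days are uniform over the stated periods.

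**1. Is the injection always in a later month?** Since 35 days exceeds the longest month (31 days), yes on schedule. Over 1,096 consecutive first-dose dates, the two doses shared a calendar month 0 times.

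**2. Where does a day-missing AE from the injection month land?** On the 1st of that month. For example, with an oral dose on 10 March 2019 and an injection on 14 April 2019, an AE recorded as April 2019 becomes 1 April 2019. Across a year end, with an oral dose on 10 December 2018 and an injection on 14 January 2019, an AE recorded as January 2019 becomes 1 January 2019. Over the 1,096 dates the imputed date preceded the injection in 96.7%, equalled it in 3.3% (injection on the 1st) and never preceded the oral dose. Lags of 28 to 60 days gave the same shares. At 28 days the doses sometimes share a month, but the AE is then set to the oral dose date, also before the injection.

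**3. How many of these placements are wrong?** Only those with true onset on or after the injection. Take a 30-day month with injection day *i* and onset day each uniform on 1 to 30, giving 30 × 30 = 900 equally likely pairs.

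- For a given *i*, the onset days on or after the injection number 31 − *i*.
- Placement is wrong when *i* ≥ 2: the sum of (31 − *i*) for *i* = 2 to 30 is 29 + 28 + … + 1 = 435.
- Misallocated share: 435/900 = 48%.
- Onset truly before the injection, correctly placed in Step 1: 435/900 = 48%.
- Injection on the 1st: 30/900 = 3%. The imputed date equals the injection date, so the AE is kept in Step 2, and it also passes the Step 1 rule.
- Among AEs with true onset on or after the injection: 435/465 = 94% are dated before it.

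**4. Year-only dates in the enrollment year.** With enrollment uniform over 365 days, mean on-study time left in that year is 365/2 = 182.5 days. Mean time left after a 35-day run-in is (365 − 35)²/(2 × 365) = 108,900/730 = 149.2 days. So 149.2/182.5 = 82% of that year's on-study time follows the injection, yet every such AE is dated to the oral dose.

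**5. What the analyses then do.** An imputed date before the injection fails the Step 2 rule in 7.3.4 and passes the Step 1 rule in 7.3.3, so the AE changes analysis.

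**The case against.** Several counter-arguments stand.

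- **The primary safety result is not affected.** Section 7.3.2 compares grade 2 or higher AEs over Steps 1 and 2 together. A reader might infer that the imputation biases this comparison. It does not: the imputed date stays on or after the oral dose, the AE stays in its randomized arm, and it is still counted.
- **The 97% is not an error rate.** A reader might take the share dated before the injection as the share misplaced. About half of those AEs did begin before the injection, and the rule places them correctly.
- **The rule is conservative in one ordinary sense.** It keeps doubtful AEs treatment-emergent as 9.2 defines that. It also applies equally to both arms, and Arm B receives placebo injections. The shortfall concerns attribution to the injectable.
- **The volume may be small.** The plan gives no count of partial dates. The day-missing problem touches one calendar month per woman, with visits at Weeks 4, 5, 6 and 9 around it. Section 8 calls data-collection failures rare, though not for AE dates in particular.
- **Step 1 person-time is not tiny in total.** About 3,350 women × 35 days / 365.25 is about 321 person-years, so one misplaced event shifts the pooled Step 1 rate by about 1/321, or 0.3 per 100 person-years.
- **Injection-site reactions are partly protected.** Appendix E identifies them by CRF terms, and the section 9.1 tables count them over injection visits. Still, 8.2 does not exempt them.

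One argument does not remove the problem: that 8.2 leaves the first dose undefined. Reading it as the first injection would break the rules for run-in AEs, so the text needs settling either way.

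**Conclusion.** The point holds for the step-specific analyses. For a woman on schedule, section 8.2 sends a day-missing AE from the first-injection month to a date before the injection, unless that was given on the 1st. It sends undated AEs, and year-only AEs in the enrollment year, to the oral dose. Sections 7.3.3 and 7.3.4 then count them in Step 1 and not in Step 2, even where onset may have followed the injection. For the injectable this is not the conservative choice that 8.2 announces.

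About 48% of day-missing AEs in that month are misallocated, assuming injection and onset days uniform over 30 days. For year-only dates in the enrollment year, about 82% of on-study time follows the injection, assuming uniform enrollment and a 35-day run-in, while all such AEs go to Step 1. These are rates per affected record. The overall effect cannot be computed, because the number of partial dates is not given, and it may be small. The documents do not support a claim that the primary safety conclusion is at risk.

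**What to change.** In section 8.2, state that the first dose is the first oral dose, and keep the present rules for the combined Steps 1 and 2 analysis. For the step-specific analyses in women who received an injection, add a second anchor:

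- If the known part of the start date is compatible with onset on or after the first injection, and neither the stop date nor other recorded information (such as the visit of report) rules it out, impute the later of the first injection date and the date that 8.2 now gives. Assign the AE to Step 2.
- Date an injection-site reaction no earlier than the injection it is recorded against.

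In 7.3.3 and 7.3.4, make the windows exclusive: Step 1 takes AEs dated before the first injection, Step 2 those on or after it. Without this, an AE imputed to the injection date passes both rules and counts twice.

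The cost is a few lines of SAP text and imputation code. The downside is that some true run-in AEs move to Step 2, up to about half (435/900) of the day-missing AEs in the injection month. If any partial dates occur, report the Step 1 analysis under the present rule as a sensitivity check.
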